### 5.3 PARTICIPANT EXCLUSION CRITERIA

Participants will be excluded if they meet any of the following criteria:

- \* Previous surgical or cosmetic procedure to the target area in the last 6 to 12 months that could interfere with the treatment procedure
- \* A study participant must not be pregnant or have been pregnant in the last 3 months
- \* A recent history of smoking (6 months)
- \* Presence of an active skin disease or condition that may affect wound healing (ie. diabetes myelitis; connective tissue disease; radiation therapy; or chemotherapy)
- \* Seizure disorder caused by bright light
- \* A history of thrombophlebitis
- \* A history of acute infections
- \* A history of heart failure
- \* Cancer, malignant disease, skin pathology, condition, or allergic reactions that could interfere with evaluation or with the use of typical ancillary medical treatments or care used before, during, or after treatments
- \* Received or is anticipated to receive antiplatelets, anticoagulants, thrombolytics, vitamin E, or anti-inflammatories within 2 weeks prior to treatment
- \* Intolerance or allergy to medications that could be prescribed before or after the procedure (eg, antibiotics, anesthesia)
- \* A history of keloids
- \* A history or evidence of poor wound healing
- \* A history of coagulative disorder or current use of anticoagulant drugs within 2 weeks of study participation
- \* Use of steroids within 2 weeks of study treatments
- \* Patients with implanted pacemaker or defibrillator, or metal pins, or prosthetic joints within 4 cm of treatment area
- \* History of psychoneurosis and/or a history of alcohol or drug abuse

After participants have provided informed consent and met the inclusion/exclusion criteria, the study procedures described in the following section will be performed.

### 5.3 STRATEGIES FOR RECRUITMENT AND RETENTION

Participants will be recruited from the site's patient database. The next appointment should be scheduled prior to the participant leaving the current appointment.

All participants who have signed an Informed Consent Form, except for screen failures, will be considered enrolled in the study. Participants who complete the study duration will be considered to have completed the study. Any participant who does not return for a scheduled follow-up visit will be contacted at least twice by telephone to

determine the cause for the missed visit and to try to get the participant scheduled for the follow-up. A new visit will be scheduled as soon as possible. All participants should be followed until completing the study follow-up or until study discontinuation (withdrawal) for other reasons. The reason for study discontinuation should be documented for each participant. Participants will be deemed “Lost-to-Follow-up” if they have not returned within six weeks after the last follow-up target. For any participant deemed lost-to-follow-up, at least three attempts to contact the participant must be documented (the attempts must be two phone calls/emails and a registered letter).

### 5.3.1 PARTICIPANT PAYMENT

Participant visits where treatments are delivered will not be compensated. Screening/Baseline visit will not be compensated. Participants in Group A, the clinical treatment arm, will be compensated \$50 for attending the 30- and 90-day follow-up visits. Participants who are selected and choose to participate in the elective skin biopsy of Group A or who are enrolled in Group B, the biopsy arm, will receive \$100 per biopsy.

## 5.4 PARTICIPANT WITHDRAWAL OR TERMINATION

All participants have the right to withdraw at any point during the study without prejudice. The investigator can discontinue any participant, at any time, if medically necessary. Participants must be discontinued from the investigation by the investigator at any time for any of the following reasons:

- Withdrawal of informed consent.
- Pregnancy (no further study-related treatments will be performed; however, the follow-up visit will be completed if the study treatments has been completed and the participant will be followed to term, called after the pregnancy, child birth, and/or pregnancy termination, and queried for abnormalities or complications).
- Any AEs for which treatment continuation would constitute an unacceptably high-risk for the participant.

The reason for any participant's withdrawal should be documented on the appropriate study-specific data form.

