#### 2.3.1.2 SAFETY VARIABLES

Prior to the first exposure, the participant's medical history will be reviewed, pregnancy history will be documented, and a physical examination of the treatment area will be conducted to ensure it is free of open wounds. At each subsequent visit, the participant will be queried about adverse events and changes in concomitant medications, and the exposure area will be visually examined.

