## 6.3.3 STUDY TREATMENT

All study treatments will be performed by the investigator, sub-investigator, or delegated clinician (ie, study exposure clinician as designated by the principal investigator). Participants will receive up to 5 treatments at the investigator's discretion using the Mosaic Ultra Treatment Parameter Guidelines as a starting point for the treatment parameters. The participants will be monitored during the exposure. The participant's pain levels will be monitored using a standard pain scale assessment (0-10). The average pain score will be recorded. Participants in Group B, the biopsy arm, will receive treatment in a discrete area such as the back, abdomen, or buttocks.

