#### **6.4 FOLLOW-UP VISITS**

Post-treatment follow-ups may occur up to 7 days post-treatment. These follow-ups are optional and may be conducted in-phone, over email, or in-person as determined by the clinician. If an optional post-treatment follow-up is determined necessary by the clinician the subject will be notified before the end of their treatment visit and the visit will be scheduled at that time. Adverse events will be evaluated at this visit. If subject has elected to participate in the biopsy portion of the study then a biopsy may also be collected at this visit.

In-person follow up visits will occur  $30\pm 7$  and  $90\pm 14$  days post final treatment. Adverse events will be assessed at these visits. Subjects will be asked to rate their satisfaction (Table 3) with their overall results as well as grade their improvement on the CGAIS (Table 4).

Subjects in Group B will then return 3 and 14 days post treatment to have an additional biopsy collected from the treated area. Subject's will then return for a final follow-up for biopsy collection between 19 and 90 days post treatment. Photos will be taken at all visits to ensure proper collection of biopsies as well as to capture the skin response.

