## 7.3 TIME PERIOD AND FREQUENCY FOR EVENT ASSESSMENT AND FOLLOW-UP

The occurrence of an AE or SAE may come to the attention of study personnel during a study visit or upon review by a study monitor. All ETEs and AEs will be captured on the appropriate data form. Information to be collected includes event description, date of onset, clinician's assessment of seriousness and severity, relationship to study device/treatment (assessed only by those with the training and authority to make a determination), actions taken, and date of event resolution. All AEs occurring while on study must be documented appropriately regardless of relationship. All ETEs/AEs assessed as "not yet resolved" must continue to be followed via telephone contact, by email, or clinic visit every 7 days or sooner (as per the physician's direction until event resolution or stabilization or tissue resection).

A pre-existing condition should not be reported as an adverse event unless there has been a substantial increase in severity or frequency of the problem that has not been attributed to natural history.

Changes in the severity of an event will be documented to allow for a determination if the event should be re-categorized from an ETE to AE.

The PI will record all reportable events, with start dates, occurring any time after informed consent is obtained until seven days (for non-serious AEs) or 30 days (for SAEs) after the last day of study participation. At each study visit, the investigator will inquire about the occurrence of ETEs/AEs/SAEs since the last visit. Events will be followed for

outcome information until resolution or stabilization.

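### Read literally, Section 5.4 takes a Group A participant with an unacceptably high-risk AE out of the study, not just off treatment, and no text expressly keeps the 30- and 90-day safety visits

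*Combined protocol and SAP*

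**What the plan says.** Section 5.4 introduces its list of mandatory reasons with "Participants must be discontinued from the investigation by the investigator at any time for any of the following reasons". One of the reasons is "Any AEs for which treatment continuation would constitute an unacceptably high-risk for the participant". The pregnancy reason in the same list stops treatment but adds follow-up. Section 7.4.4(c) likewise stops treatment for a pregnancy that begins mid-course and continues follow-up.

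Section 5.3 (Strategies for Recruitment and Retention) gives the general rule: "All participants should be followed until completing the study follow-up or until study discontinuation (withdrawal) for other reasons".

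Section 6.4 places Group A's in-person visits at 30±7 and 90±14 "days post final treatment. Adverse events will be assessed at these visits". Table 5 in Section 6.2 adds photographs at both. Section 2.3.1.2 says that at each visit the participant is asked about AEs "and the exposure area will be visually examined".

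Under Section 7.3, unresolved events "must continue to be followed via telephone contact, by email, or clinic visit every 7 days or sooner", until they resolve or stabilize. New events are recorded "until seven days (for non-serious AEs) or 30 days (for SAEs) after the last day of study participation".

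On dose, Section 6.3.3 says "Participants will receive up to 5 treatments at the investigator's discretion".

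**The concern.** Stopping treatment and leaving the study are different acts, and Section 5.4 uses the second where the first would do. The clause can act only while sessions remain, so it mainly concerns Group A partway through its course; Group B has a single session. Those it removes are the participants with the most worrying reactions. They stay in the safety analysis, because Sections 9.1 and 9.2 include everyone treated, completely or not. They also bear on Group A's second success criterion in Section 4.4, an acceptable AE and side effect profile.

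Section 2.3.1 lists scarring, keloid formation and possibly permanent discoloration among the known risks. These are best judged by looking at the skin and comparing standardized photographs. If the 90-day visit falls away, the late skin outcome may go unrecorded in the participants for whom it matters most.

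**Working it through.** **Step 1. Does any text keep the two visits?**

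- Section 5.4, pregnancy reason, and Section 7.4.4(c): follow-up after treatment stops is stated. The AE reason has no matching clause.
- Section 5.3 (Strategies for Recruitment and Retention): follow-up runs to completion or to discontinuation. It adds nothing after discontinuation.
- Section 7.3: the open event is followed at least every 7 days, but telephone or email is enough, and contact ends once the event is resolved or stable.
- Section 7.4.1: a reported problem is followed to the last study visit or to its resolution, and not after the final visit. No 90-day visit is required after discontinuation.
- Section 2.3.1.1: covers an exposure that is not tolerated. Its and/or wording sets no clear minimum, and the period it names is 30 days.
- Section 6.3.5: an unscheduled visit with photographs is arranged if the participant reports side effects such as blistering, strong pain or signs of infection. It depends on that report, and late scarring, keloid and discoloration are not on its list.

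The triggering event is therefore followed, but the scheduled visits are not expressly kept.

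**Step 2. How far does recording of new events reach?** Days are counted from the last exposure.

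Inputs: 90±14-day visit (Section 6.4); recording for 7 days (non-serious) or 30 days (SAE) after participation ends (Section 7.3); sessions 2–6 weeks apart, so at most 6 × 7 = 42 days (Section 6.3).

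- 90-day visit window: 90 − 14 = 76 to 90 + 14 = 104.
- Last day of participation needed for recording to reach day 76: non-serious 76 − 7 = 69; SAE 76 − 30 = 46.

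| Case | Non-serious AE recorded to | SAE recorded to |
|---|---|---|
| Participation ends at the decision, taken on day 0–42 (assumed) | 0 + 7 = 7 to 42 + 7 = 49 | 0 + 30 = 30 to 42 + 30 = 72 |
| Stays on study to the 90-day visit | 76 + 7 = 83 to 104 + 7 = 111 | 76 + 30 = 106 to 104 + 30 = 134 |

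In the first row every value falls before day 76. If the Section 7.3 contacts count as participation, recording closes later. It then reaches day 76 when the event stays open after the decision for a further 69 − 42 = 27 to 69 − 0 = 69 days (non-serious) or 46 − 42 = 4 to 46 − 0 = 46 days (SAE). The gap is therefore widest for new non-serious effects after an event that closes early.

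**Step 3. Effect on a reported rate.** With 180 participants in Group A, one participant is 1/180 = 0.56 percentage points of an event-specific late rate. The any-AE participant rate changes by 0, because each of these participants already has the AE that triggered removal.

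**The case against.** The strongest reply is that the wording need not be read so strictly. Pregnancy stands under the same lead-in sentence and still carries follow-up, so discontinuation from the investigation cannot by itself mean the end of all contact. Section 6.4 counts its visits from the final treatment, and the last session a removed participant received is their final treatment. An investigator may also simply stop at fewer than five sessions without invoking Section 5.4. Sections 7.3, 7.4.1, 2.3.1.1 and 6.3.5 together give real follow-up of the reaction itself.

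Much of this stands. A reader might infer that the protocol definitely drops these participants from all safety follow-up; the documents do not support that, because the event remains under follow-up and the phrase is open to a milder reading. A reader might also infer that Group A's AE rate would be understated overall. That does not follow either, since the any-AE participant rate cannot move.

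What does not stand is that the gap is closed. The protocol states follow-up for pregnancy and not for the AE reason, the general rule ends follow-up at discontinuation, and none of the other sections requires the 30- and 90-day visits. A site that applies Section 5.4 as written could reasonably exit the participant.

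**Conclusion.** The point holds as a cheap improvement. On a literal reading, Section 5.4 can cost a Group A participant with sessions remaining the scheduled 30- and 90-day skin examinations and photographs. What may be lost is a new non-serious late effect or a late change in a closed event, up to 0.56 percentage points per participant on an event-specific rate at full enrolment, together with the late outcome for that person.

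This rests on the literal reading of Sections 5.4 and 5.3. The window figures rest further on the assumed decision day and on whether Section 7.3 contacts count as participation. The documents give neither a removal rate nor a late-AE rate, so the total effect cannot be estimated. It is probably modest: this is a pilot with descriptive summaries (Section 9.3), and the AE criterion in Section 4.4 has no numerical threshold. It would go too far to say that the criterion is invalidated.

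**What to change.** - **Section 5.4:** make this AE reason a discontinuation of study treatment only. Keep the participant on the existing 30- and 90-day AE assessments and photographs, counted from the last exposure, unless consent is withdrawn. The decision to stop treatment stays with the investigator.
- **Section 5.3 (Strategies for Recruitment and Retention):** align the follow-up rule with this.
- **Section 2.3.1.1:** replace the and/or 30-day wording with follow-up to resolution or stabilization and, in Group A, at least through the 90-day visit.
- **Sections 9.1 and 9.2:** state that participants stopped for an AE do not count as having received complete treatment for the primary image set. Complete is not defined, and treatment is up to five sessions at discretion, so without this sentence their new day-90 photographs could arguably bring them into that set. With it, the set is unaffected.

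The cost is protocol wording, plus up to two visits already in Table 5 and $50–$100 per affected participant. Section 5.3.1 does not say whether the $50 covers both visits or each one (2 × $50 = $100).

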### 6.2 STUDY SCHEDULE

Table 5: Study Schedule

Group A – Clinical Treatment Arm – Schedule and Planned Activities

	Screening	Treatment	Post Treatment Follow-Up (optional) 1-7days post Tx	Follow-Up 30-day post final TX	Follow-Up 90-day post final TX
Visit Number	1	2, 4, 6, 8, 10	3, 5, 7, 9, 11	12	13
Study Day #	0	0 – 140	1-147	170 (±7)	230 (±14)
Screening Activities	X				
Pregnancy Test	X	X			
Photographs		X	X	X	X
Device Treatment		X			
Biopsy (optional)		X	X	X	X
Adverse Event Assessment		X	X	X	X
Subject Evaluations				X	X
Physician Evaluation				X	X

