## 6.3 STUDY TREATMENT

Participants in Group A, the clinical treatment arm, will receive up to 5 treatments at the investigator's discretion using the Mosaic Ultra Treatment Parameter Guidelines as a starting point for the treatment parameters. Treatments will occur 2-6 weeks apart depending on the clinical indication being treated. Participants in Group B, the biopsy arm, will only receive one treatment with pre-determined parameters in a discrete area of the body (such as abdomen, buttocks, back).

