### 7.4.4 REPORTING OF PREGNANCY

Each pregnancy that starts during the participant's study participation must be reported by the investigator to the Sponsor within 24 hours of learning of its occurrence. Pregnancies and pregnancy follow-up should be reported on an Adverse Event form. Pregnancy follow-up should describe the outcome of the pregnancy, including any voluntary or spontaneous discontinuation; details of the birth; the presence or absence of any congenital abnormalities, birth defects, maternal or newborn complications, and their relationship to the device or treatment/exposure. Each pregnancy must be reported as a non-serious AE if the participant has received at least one study treatment/exposure. The following criteria should be followed:

- a. If a participant becomes pregnant after the Baseline visit and all study treatments/test spot exposure have been completed, the participant should continue to be followed for the duration of the pregnancy.
- b. If a participant becomes pregnant after the Baseline visit but before any study treatments/test spot exposures, the participant should be exited from the study.

- c. If a participant becomes pregnant after the Baseline visit but before all study treatments/test spot exposures have been completed, additional study treatments/test spot exposures should be discontinued and the participant should continue to be followed for the duration of the pregnancy.

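### Section 5.4 ties the follow-up visit after a pregnancy to completed treatment, so a Group A participant whose course is cut short may miss her 30- and 90-day skin checks, although Section 6.4 can be read to keep them

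*Combined protocol and SAP*

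**What the plan says.** Section 5.4 lists pregnancy under the sentence "Participants must be discontinued from the investigation by the investigator at any time for any of the following reasons". The pregnancy item stops further treatment and then makes an exception for follow-up: "the follow-up visit will be completed if the study treatments has been completed and the participant will be followed to term". It also provides a call after the pregnancy to ask about problems.

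Section 7.4.4(c) deals with a pregnancy that begins before all treatments have been given: "additional study treatments/test spot exposures should be discontinued and the participant should continue to be followed for the duration of the pregnancy". It does not mention the 30- or 90-day visits.

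Section 6.4 sets in-person visits for Group A at 30±7 and 90±14 "days post final treatment. Adverse events will be assessed at these visits". Table 5 in Section 6.2 heads the last column "Follow-Up 90-day post final TX". Neither makes the visits conditional on a completed course.

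Section 6.3 says that Group A participants "will receive up to 5 treatments at the investigator's discretion", and that "Treatments will occur 2-6 weeks apart depending on the clinical indication being treated". Group B receives one treatment.

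Section 2.3.1.2 attaches the safety checks to visits: at each one after the first exposure the participant is asked about adverse events and medication changes, "and the exposure area will be visually examined". Section 9.1 includes participants with incomplete treatment in the safety analysis.

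**The concern.** A participant who has been exposed to the laser and then stops because of pregnancy should have her skin checked on the same schedule as everyone else. Section 5.4 gives that assurance only where treatment was completed. Without it, she counts in the safety denominator but may have no scheduled examination after her last treatment or her last in-person visit.

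Section 2.3.1 lists permanent discoloration, scarring and keloid among the risks. One of these could appear after the last in-person check, and nothing scheduled would then look for it. Two sections that point different ways also leave the three sites free to act differently in the same situation.

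**Working it through.** **Reading the sections together**

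1. Section 5.4 discontinues the participant and then restores the follow-up visit on a condition. The text does not say that the visit is kept only on that condition. But an exception introduced by a contrast and carrying a condition is naturally read as not applying when the condition fails.
2. The recruitment and retention section (the second one numbered 5.3) follows participants until they finish follow-up or are discontinued. Because 5.4 makes pregnancy a discontinuation, this supports the restrictive reading.
3. Section 7.4.4(c) continues follow-up through the pregnancy. The content that 7.4.4 specifies is pregnancy and birth outcome, not skin examination. Its silence on the visits settles nothing either way: 7.4.4(a) is equally silent for completed courses, where 5.4 does keep the visit.
4. Section 6.4 and Table 5 count from the final treatment. If that means the last treatment received, both visits survive. If it means the last planned treatment, there is no date to count from.
5. With the number of treatments left to discretion in 6.3, a completed course has no fixed meaning. Yet 7.4.4(c) recognises an incomplete course as a separate case, so a shortened course cannot simply be assumed to count as complete.
6. Group B is outside the problem: its single treatment is complete on day 0.

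The two readings are both available, and the restrictive one loses the visits.

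**Scheduled skin observation lost per affected participant**

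Inputs, in days from the last treatment received:
- 90-day visit window, 90±14 (6.4): day 76 to 104.
- 30-day visit window, 30±7 (6.4): day 23 to 37.
- Next treatment visit, 2 to 6 weeks later (6.3), with a pregnancy test (Table 5): day 14 to 42.
- Optional post-treatment contact, which may be in person (6.4): up to day 7.

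Formula: day of the 90-day visit minus day of the last in-person check.
- Pregnancy found at the next treatment visit: 76 − 42 = 34 to 104 − 14 = 90 days.
- Pregnancy found between visits: 76 − 7 = 69 to 104 − 0 = 104 days.
- Both routes together: 34 to 104 days. Taking the 90-day visit at its nominal day: 90 − 42 = 48 to 90 − 0 = 90 days.

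At a six-week interval, detection falls on day 42, after the 30-day window closes on day 37. Only the 90-day visit could then be kept.

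**Number of participants affected**

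The documents give neither a pregnancy rate nor a sex mix, so this is an assumption throughout: 50–90% of the 180 Group A participants able to become pregnant, at 1–5% per year. A single-treatment course carries no risk of being cut short, so the lower end is 0. With two treatments two weeks apart (14 days), the smallest value is 180 × 0.5 × 0.01 × 14/365 = 0.03. At the top, Table 5's 140-day treatment period gives 180 × 0.9 × 0.05 × 140/365 = 3.1. Four six-week intervals (4 × 42 = 168 days) give 180 × 0.9 × 0.05 × 168/365 = 3.7. The range is 0 to about 3.7, and its upper end needs every input at its extreme.

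**The case against.** The strongest reply is that no sentence forbids the visits. Section 5.4 itself ends treatment at pregnancy, so the last treatment received becomes the final one, and 6.4 then schedules both visits from it. Discretion over the number of treatments lets an investigator call the course finished. This stands as far as it goes. A reader might infer from 5.4 that the plan bars follow-up visits after a partial course, and the documents do not support that. What they show is two sections that can be applied in opposite ways.

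A reader might also infer that a late skin effect could surface only at an unscheduled visit or in the call after the pregnancy. That is too strong. Sections 5.4 and 7.4.4(c) require contact throughout the pregnancy, which for one carried to term would normally run past day 90. Section 7.3 requires unresolved events to be followed every seven days or sooner, and 7.4.1 also calls for follow-up of reported problems. What remains is a new effect that she does not report. None of those provisions schedules an examination to find one.

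The exclusions for keloid history and poor wound healing make two of the listed harms less likely. The study is a pilot of a device that Section 2.2 classes as non-significant risk. Both points lower the weight of the concern but do not resolve the conflict between the sections.

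**Conclusion.** The point holds as a conflict over safety follow-up with a limited consequence. Followed as written, 5.4 can remove the scheduled adverse event check and skin examination from a treated Group A participant whose course stops for pregnancy, while 6.4 and Table 5 can be read to keep them. The loss is about 34 to 104 days of scheduled skin observation per affected participant, which follows from the visit windows and treatment intervals alone. The harm left uncovered is mainly a late-onset skin effect that she does not report.

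Few participants are likely to be affected, but the count rests wholly on assumed rates. No efficacy result changes: Section 9.1 admits only complete treatment to the efficacy analysis, and a course judged complete keeps its visit under 5.4 anyway. The change is worth making because the participants concerned are exposed, are counted in the safety analysis, and can be covered at very little cost. Confidence is medium, because the loss depends on which of the two readings a site adopts.

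**What to change.** In Section 5.4, delete the condition that study treatments be completed. In 5.4 and 7.4.4(c), state that pregnancy stops treatment, but that any participant who has received at least one treatment attends the existing 30- and 90-day visits, timed from the last treatment received. Add that no optional biopsy is taken and that a visit whose window has already passed is omitted.

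The cost is a wording change in two places and at most two visits of an existing type per affected participant, at the follow-up payment already in Section 5.3.1. Under the assumed rates that is 0 to about 7 visits in all (2 × 3.7 = 7.4). No new procedure or staff is needed, and no other section has to change.
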